ESC	European Society of Cardiology
FAS	Full Analysis Set
FLARE	FlowTriever Clinical Embolectomy Clinical Study
FT2	FlowTriever2 Catheter
HIT	Heparin-induced thrombocytopenia
INR	International normalized ratio
IRB	Institutional Review Board
ISS	Injury Severity Score
ITT	Intent-To-Treat
LV	Left ventricle
MAE	Major adverse event
MITT	Modified Intent-To-Treat
PE	Pulmonary embolism
PESI	Pulmonary Embolism Severity Index
RV	Right ventricle
RV/LV	Right ventricular to left ventricular diameter ratio
SADE	Serious Adverse Device Effect
SAE	Serious Adverse Event
SBP	Systolic Blood Pressure
SIR	Society of Interventional Radiology
SPESI	Simplified Pulmonary Embolism Severity Index
TLF	Tables, lists, and figures
UADE	Unanticipated Adverse Device Effect
USADE	Unanticipated Serious Adverse Device Effect
VARC-2	Valve Academic Research Consortium-2

1. Description of Study Objectives

The primary study objective is to evaluate the safety and effectiveness of the FlowTriever2 Catheter for the treatment of acute pulmonary embolism (PE).

2. Study Design

The study is a prospective, non-randomized, single-arm, multicenter, observational study to evaluate the safety and effectiveness as the study endpoints of the FlowTriever2 Catheter in patients eligible for endovascular treatment of acute PE. The endpoints will be evaluated in descriptive manner and will not be used to determine study success.

2.1. Primary Safety Endpoints

The study's primary safety endpoint is incidence of Serious Adverse Events (SAE), which is defined as a composite of:

- Mortality through 48 hours after the index procedure related to FlowTriever2 Catheter
- Major bleeding through 48 hours after the index procedure related to FlowTriever2 Catheter
- Intra-procedural device or procedure-related adverse events, including:
 - Clinical deterioration defined by hemodynamic or respiratory worsening
 - Pulmonary vascular injury related to FlowTriever2 Catheter
 - Cardiac injury related to FlowTriever2 Catheter

2.2. Primary Effectiveness Endpoint

The study's primary effectiveness endpoint is the change in mean pulmonary arterial pressure from baseline pre-procedure to post-procedure.

2.3. Secondary Safety Endpoints

The study's secondary safety endpoints will include incidence of adjudicated adverse events, including:

- All-cause mortality through the 30-day visit (visit window = 30 days from procedure -5 / +15 days)
- Device-related SAE through the 30-day visit (visit window = 30 days from procedure -5 / +15 days)
- Symptomatic recurrence of pulmonary embolism through the 30-day visit (visit window = 30 days from procedure -5 / +15 days)

3.1. Study Enrollment Criteria

Only patients who meet all inclusion criteria and none of the exclusion criteria are considered eligible for enrollment. The decision to use the FlowTriever2 Catheter will occur prior to the procedure and written informed consent will be obtained prior to all study-specific procedures. The enrollment period is expected to last over a period of approximately 12 months. Each study subject will actively participate for up to 30 days (-5 / +15 days) following treatment. Study participation includes screening, baseline, treatment, 48-hour visit, and 30-day follow-up.

If the FlowTriever2 Catheter is not inserted into the vasculature, the subject is considered a screen failure (not meeting inclusion criteria for use of FT2) and is not enrolled into nor entered the EDC.

3.1.1. Inclusion Criteria

Subjects must meet all the following inclusion criteria to be considered eligible for enrollment.

1. Age \geq 18 and \leq 75 years
2. Clinical signs and symptoms consistent with acute PE
3. PE symptom duration \leq 14 days
4. CTA evidence of proximal PE (filling defect in at least one main or lobar pulmonary artery)

5. RV/LV ratio of ≥ 0.9 (**NOTE:** Enrollment qualification assessment based on Investigator's interpretation of RV/LV ratio)
6. Systolic blood pressure ≥ 90 mmHg (initial SBP may be ≥ 80 mmHg if the pressure recovers to ≥ 90 mmHg with fluids)
7. Stable heart rate < 130 BPM prior to procedure
8. Patient is deemed medically eligible for interventional procedure(s), per institutional guidelines and/or clinical judgment.
9. FlowTriever2 Catheter enters the vasculature

3.1.2. Exclusion Criteria

Subjects must not meet any of the following general exclusion criteria.

1. Thrombolytic use within 30 days of baseline CTA
2. Pulmonary hypertension with peak pulmonary artery pressure > 70 mmHg by right heart catheterization
3. Vasopressor requirement after fluids to keep pressure ≥ 90 mmHg
4. FiO₂ requirement $> 40\%$ or > 6 LPM to keep oxygen saturation $> 90\%$
5. Hematocrit $< 28\%$ (**NOTE:** hematocrit required within 6 hours of index procedure)
6. Platelets $< 100,000/\mu\text{L}$
7. Serum creatinine > 1.8 mg/dL
8. INR > 3
9. Major trauma Injury Severity Score (ISS) > 15
10. Presence of intracardiac lead in the right ventricle or right atrium placed within 6 months
11. Cardiovascular or pulmonary surgery within last 7 days
12. Actively progressing cancer
13. Known bleeding diathesis or coagulation disorder
14. Left bundle branch block
15. History of severe or chronic pulmonary arterial hypertension
16. History of chronic left heart disease with left ventricular ejection fraction $\leq 30\%$
17. History of uncompensated heart failure
18. History of underlying lung disease that is oxygen dependent
19. History of chest irradiation
20. History of heparin-induced thrombocytopenia (HIT)
21. Any contraindication to systemic or therapeutic doses heparin or anticoagulants
22. Known anaphylactic reaction to radiographic contrast agents that cannot be pretreated
23. Imaging evidence or other evidence that suggests, in the opinion of the Investigator, the Subject is not appropriate for mechanical thrombectomy intervention (e.g., inability to navigate to target location, predominately chronic clot, or non-clot embolus)
24. Life expectancy of < 90 days, as determined by Investigator
25. Female who is pregnant or nursing
26. Current participation in another investigational drug or device treatment study

4. Incomplete Date Handling and Missing Data

Incomplete dates will follow the following imputation assignment rules:

1. If day is missing but month and year are present, the day will be set to the first date of the month.
2. If both day and month are missing but year is present, then January 1st will be used as imputed value.
3. If year is missing, then the date is considered missing. In general, missing data points are not imputed.

For the primary safety endpoints, missing data are imputed with a range of possible-worse case scenarios and reported the corresponding incidence rates using a tipping point analysis assuming missing at random. For the primary effectiveness endpoints, missing data at pre- or post-procedures are imputed with values resampled from the non-missing data with replacements assuming missing at random. A number (e.g., 10,000) of replicates of data with imputed values can be generated and the mean and 95% confidence interval based on the averaged change in each replicate are reported. No imputations are performed in the secondary endpoints.

5. Statistical Methods and Analysis

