# 6.2.4 30-DAY VISIT (-5 TO + 15 DAYS)

The sites will complete the following assessments either remotely or in-person on the subjects at the 30-Day Visit (visit window = 30 days from procedure -5 days / +15 days):

- Physical examination and vitals
- Record adverse events, as applicable
- Record concomitant medications
- Complete Study Exit form

If the 30-Day Visit is completely remotely, the physical examination and vitals are not required.

Subjects who expire during their participation will be documented on an Adverse Event form and Study Exit form. Sites will fill out the Study Exit form for all enrolled subjects, regardless of reason, at the 30-Day Visit.

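### The SAP's partial-date rule has no lower bound at the procedure date, so a partly dated event could be placed before Time 0 or wrongly inside the 48-hour safety window

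*SAP*

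**What the plan says.** SAP section 4 (Incomplete Date Handling and Missing Data) sets three rules for incomplete dates:

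- Day missing: "If day is missing but month and year are present, the day will be set to the first date of the month".
- Day and month missing: "If both day and month are missing but year is present, then January 1st will be used as imputed value".
- Year missing: "If year is missing, then the date is considered missing. In general, missing data points are not imputed".

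The rules are not limited to any type of date. They do not mention the procedure date, event onset or the endpoint windows. Later in the same section, the SAP says that secondary endpoints receive no imputation and that missing primary safety data are handled by worse-case scenarios in a tipping-point analysis.

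Two components of the primary safety endpoint in SAP 2.1 have a clock limit: "Mortality through 48 hours after the index procedure related to FlowTriever2 Catheter" and "Major bleeding through 48 hours after the index procedure related to FlowTriever2 Catheter". The third, "Intra-procedural device or procedure-related adverse events, including" clinical deterioration and vascular or cardiac injury, is tied to the procedure and not to a day count. The secondary safety endpoints in SAP 2.3 run to the 30-day visit, for example "All-cause mortality through the 30-day visit (visit window = 30 days from procedure -5 / +15 days".

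The footnotes to Table 1 in protocol section 6.2 define Time 0 as the moment the FlowTriever2 Catheter enters the vasculature.

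**The concern.** A first-of-month default suits medical history. For an event that can only follow a procedure, it moves the date in one direction: earlier, often past the procedure.

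Two examples show the two errors. With a procedure on 17 May and a bleed on 18 May recorded only as May, the rule gives 1 May, 16 days before Time 0. With a procedure on 30 January and an event on 10 February recorded only as February, the rule gives 1 February, which is day 2 and inside 48 hours.

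The first result also conflicts with the protocol's data flow. Section 8.2 starts adverse-event collection after consent and enrolment, and section 5.3 makes catheter insertion part of enrolment. A study event dated before Time 0 should therefore not exist, yet the rule can create one.

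At stake is the reported 48-hour rate. A true early event could drop out, or a later event could be counted. The rule also turns an uncertain date into an apparently complete one, so nothing sends that subject to the tipping-point analysis. Dates learned after discharge are the likelier ones to be partial, since at day 30 "The sites will complete the following assessments either remotely or in-person on the subjects at the 30-Day Visit".

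**Working it through.** **The plan's own figure.** The documents give no figure for the date rule. The one design figure is power in SAP 5.1: n=50, 11% against 25%, one-sided alpha 0.05, at least 80%. It reproduces with an exact binomial and a limit of 7 events: P(X ≤ 7 | 50, 0.25) = 0.0453 and P(X ≤ 7 | 50, 0.11) = 0.8207. For scale, one subject is 1/50 = 2 percentage points; 7 events is 14% and 8 events is 16%.

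**Inputs for the date rule.** The two imputation rules (SAP 4), the 48-hour limit (SAP 2.1), Time 0 (protocol 6.2), and follow-up to day 30, with a visit window reaching day 30 + 15 = 45 (SAP 2.3).

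**Assumptions (not in the documents).** Procedure dates are uniform over the 365 days of a non-leap year. Each lag L in whole days is equally likely within the stated range. 48 hours means days 0 to 2. The date is partial.

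**Formula.** Imputed study day d = (first day of the event's month) − (procedure date). If d < 0, the event is dated before the procedure.

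**True day 0-2 events, by hand.** The imputed date is not before the procedure only if the procedure was on the 1st or the event fell in the next month.

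- L = 0: 12 procedure dates of 365 (the 1sts).
- L = 1: 24 (the 1sts and the last days of months).
- L = 2: 36 (those and the second-last days).

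Total 72 of 3 × 365 = 1,095, or 6.6%. The other 93.4% are dated before the procedure.

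**True day 3-30 events, by hand.** For L up to 27, the share not dated before the procedure is 12(1 + L)/365. Of all dates, 36/365 = 9.9% give d of 0 to 2 (procedures on the 1st, last or second-last day of a month). The mean of 1 + L over L = 3 to 30 is 17.5, so about 12 × 17.5/365 = 57.5% are not before the procedure and 42.5% are. Lags above 27 differ slightly because of month lengths, so the table uses full enumeration.

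| Missing part | True event day | Dated before procedure | Placed on days 0-2 | Placed after day 2 |
|---|---|---|---|---|
| Day | 0-2 | 93.4% | 6.6% (correct) | 0% |
| Day | 3-30 | 42.6% | 9.8% (wrong) | 47.7% (correct) |
| Day | 3-45 | 27.7% | 6.5% (wrong) | 65.8% (correct) |
| Day and month | 0-2 | 99.5% | 0.5% (correct) | 0% |
| Day and month | 3-30 | 95.2% | 0.8% (wrong) | 4.0% (correct) |

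**Effect on the 48-hour count.** This depends on a programming choice that the SAP does not state.

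- Window coded as 0 ≤ d ≤ 2: 93.4% of partly dated true 48-hour events are lost.
- Window coded as d ≤ 2 only: none is lost, but 42.6% + 9.8%, about 52%, of partly dated day 3-30 events are counted.

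**Lower bound at the procedure date.** Replacing the imputed date by the later of itself and the procedure date keeps 100% of true day 0-2 events. It also puts 52.3% of partly dated day 3-30 events inside 48 hours, so the bound alone exchanges one error for the other.

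**The case against.** The strongest reply is that the documents may never use an imputed date to decide an endpoint. The protocol calls the primary safety endpoint adjudicated (section 4.2). The Clinical Events Committee reviews every adverse event, can ask for source documents, and overrules the investigator (section 8.7). Onset is a recorded item for every event (section 8.2). A subject discharged before 48 hours is phoned about serious events up to 48 hours (section 6.2.3), and that call itself settles window membership. The endpoints are descriptive and do not determine success (SAP section 2).

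Most of this stands, and it limits exposure. It does not close the gap. Section 8.7 gives the committee validation and relatedness to device or procedure; it does not say that its timing overrides an imputed date. SAP 2.1 omits the word adjudicated for the primary endpoint. A descriptive rate is still what the study will report.

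Three stronger readings are tempting, and the documents do not support them:

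- **That events will be misclassified, or usually are.** This needs partial onset dates and a window derived from them; neither is stated. For true day 3-45 events, 65.8% stay correctly after 48 hours.
- **That the 30-day endpoints are compromised.** The rule only moves dates earlier, so it cannot push an event past the upper limit, and SAP section 4 says secondary endpoints receive no imputation. That sentence does sit awkwardly with a rule for all incomplete dates.
- **That a back-dated thrombolytic would make a subject ineligible.** SAP section 3 allows later removal for failed criteria, but nothing ties removal to imputed dates. Eligibility rests on data available at enrolment, and thrombolytics are recorded visit by visit.

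**Conclusion.** The rule is unsuitable for on-study event dates as written. If it is used to place a partly dated event, it gives a date before Time 0 for 93% of true 48-hour events. For true day 3-30 events it gives 43% before the procedure and 10% wrongly within 48 hours; for days 3-45, 28% and 6.5%. These shares rest on uniform procedure dates and lags, on 48 hours meaning days 0 to 2, and on the day being missing. They are conditional on a partial date.

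The number of partial dates is not given and is probably low for in-hospital events. A year-only date within at most 45 days of follow-up is a remote case. The 48-hour rate changes only if the affected event is a FlowTriever2-related death or major bleed; each such subject is 2 percentage points at n=50. No hypothesis test is relied on, so the risk is bias in a reported rate and not type I error. This is a modest point that is cheap to correct.

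**What to change.** Amend SAP section 4 for the start dates of adverse events, deaths and concomitant medications on study:

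1. Source-verified or committee-adjudicated timing decides whether an event falls in a window.
2. Where that is unavailable, impute the later of the procedure date and the first day of the known month or year, unless records show earlier onset.
3. List every event handled this way, and report the 48-hour rate under both the earliest and the latest possible date.
4. Keep the first-of-month and 1 January rules for medical history only.
5. Reconcile the date rule with the statement in the same section that secondary endpoints receive no imputation.

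The cost is a few sentences, one listing and one extra row in the safety table, with no new data. The downside is that the earliest-date rate may count later events as 48-hour events: about 52% of partly dated day 3-30 events under the assumptions above. That is why both bounds should be reported and adjudicated timing should come first.

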5.1. Sample Size

The sample size of 50 subjects was adopted to confirm the FlowTriever2 Catheter performance. Given the sample size, at least 80% power can be achieved under one-sample fixed design with one-sided alpha = 0.05 for assuming observed FT2 safety event proportions of 11% compared to the hypothesized performance goal of 25% from FLARE. Descriptive statistics on safety and effectiveness endpoints will be provided based on all subjects to conclude the study objectives, no hypothesis testing was relied. Sensitivity analysis will be performed on a sub-population of the 50 subjects that did not receive adjunctive thrombolytics.

5.2. Primary Safety Endpoint Analysis

The primary safety endpoint analysis is performed by assessing the incidence rate of the composite endpoint of SAE, including device-related mortality through 48 hours, device-related major bleeding through 48 hours, intra-procedural device or procedure-related adverse events.

5.3. Primary Effectiveness Endpoint Analysis

The primary effectiveness endpoint analysis is performed by assessing the means, standard deviations, medians, and inter-quartile ranges of the mean pulmonary arterial pressure changes and/or percentage change between pre- and post-procedure.

5.4. Secondary Safety Endpoint Analysis

The secondary safety endpoint analysis is performed by assessing the incidence rates of adjudicated adverse events, including all-cause mortality through the 30-day visit, device-related SAE through the 30-day visit, and symptomatic recurrence of pulmonary embolism through the 30-day visit.

5.5. Secondary Effectiveness Endpoint Analysis

The secondary effectiveness endpoint analysis is performed by assessing the means, standard deviations, medians, and inter-quartile ranges of the systolic pulmonary arterial pressure changes and/or percentage change between pre- and post-procedure. Adjunctive thrombolytic use is reported as numbers and percentages.

6. Terms and Definitions

Term	Definition
Primary Safety Definitions	
Clinical Deterioration	Clinical deterioration will include treatment-related events, such as unplanned endotracheal intubation, unexpected requirement for mechanical ventilation, arterial hypotension (>1 hour or requiring vasopressors) or shock, cardiopulmonary resuscitation, persistent worsening in oxygenation, and emergency surgical embolectomy.
Device Related Death	Device-related death is defined as any death directly related to the device not performing as expected. Device-related death would include death from: 
 • Vascular or cardiovascular injury • Device malfunction • Device-induced cardiac arrhythmia
Life Threatening or Disabling Bleeding (VARC-2)	
 • Fatal bleeding, OR • Bleeding in a critical organ, such as intracranial, intraspinal, intraocular, or pericardial necessitating pericardiocentesis, or intramuscular with compartment syndrome, OR • Bleeding causing hypovolemic shock or severe hypotension requiring vasopressors or surgery, OR • Overt source of bleeding with drop in hemoglobin ≥ 5 g/dL or whole blood or packed red blood cells (RBCs) transfusion ≥ 4 units*
Major Bleeding (VARC- 2)	Overt bleeding that is: 
 • Associated with a drop in the hemoglobin level of at least 3 g/dL, OR • Requires transfusion of 3 units of whole blood/RBC, OR • Causes hospitalization, permanent injury, or requiring surgery, AND • Does not meet criteria of life-threatening or disabling
Minor Bleeding (VARC- 2)	Any bleeding worthy of clinical mention (e.g., access site hematoma) that does not qualify as life-threatening or disabling bleeding or major bleeding.
Pulmonary Vascular Injury	Pulmonary vascular injury is defined as perforation or injury of a major pulmonary arterial branch during the index procedure requiring intervention, including but not limited to blood transfusion, open or endovascular intervention, to avoid permanent injury.
Cardiac Injury	Cardiac injury is defined as any damage to the heart during the index procedure requiring intervention, including but not limited to blood transfusion, open or endovascular intervention, to avoid permanent injury.
Additional Definitions	
Adverse Event (AE)	
An Adverse Event (AE) is an untoward medical occurrence, unintended disease or injury, or untoward clinical signs (including abnormal laboratory findings) in subjects, users or other persons, whether or not related to the investigational medical device and whether anticipated or unanticipated (ISO 14155:2020, 3.2).
 
NOTE 1: This definition includes events related to the investigational medical device.
 
NOTE 2: This definition includes events related to the procedures involved.

Serious Adverse Event (SAE)	An AE that led to any of the following: 
 • death, • serious deterioration in the health of the subject, users or other persons as defined by one or more of the following: 
 ◦ a life-threatening illness or injury, or

Term	Definition
	
 ○ a permanent impairment of a body structure or a body function, including chronic disease, or ○ in-patient or prolonged hospitalization, or ○ medical or surgical intervention to prevent life- threatening illness or injury or permanent impairment to a body structure or a body function, ● fetal distress, fetal death or a congenital abnormality or birth defect including physical or mental impairment 
NOTE 1: Planned hospitalization for a pre-existing condition, or a procedure required by the CIP, without serious deterioration in health, is not considered an SAE. (ISO 14155:2020, 3.45)

Minor Complications (SIR Classification)	
Minor complications:
 
 ● No therapy, no consequence ● Nominal therapy, no consequence (includes overnight admission for observation only)
Major Complications (SIR Classification)	
Major complications:
 
 ● Require therapy, minor hospitalization (≤ 48 hours) ● Require major therapy, unplanned increase in level of care, prolonged hospitalization (>48 hours) ● Permanent adverse sequelae ● Death
Adverse Device Effect (ADE)	
AE related to the use of an investigational medical device
 
NOTE 1: This definition includes AEs resulting from insufficient or inadequate instructions for use, deployment, implantation, installation, or operation, or any malfunction of the investigational medical device.
 
NOTE 2: This definition includes any event resulting from an error use or from intentional misuse of the investigational medical device.
 
NOTE 3: this includes 'comparator' if the comparator is a medical device. (ISO 14155:2020, 3.1)

Serious Adverse Device Effect (SADE)	Adverse device effect that has resulted in any of the consequences characteristic of a serious adverse event. (ISO 14155:2020, 3.44)
Unanticipated Serious Adverse Device Effect (USADE) (pre-market term only)	USADE is a serious adverse device effect which by its nature, incidence, severity or outcome has not been identified in the current risk assessment. (ISO 14155:2020, 3.51)
Anticipated Serious Adverse Device Effect (ASADE) (pre-market term only)	ASADE is a serious adverse device effect which by its nature, incidence, severity or outcome has been identified in the risk assessment. (ISO 14155:2020, 3.51)
Unanticipated Adverse Device Effect (UADE) (pre-market term only)	Any serious adverse effect on health or safety or any life- threatening problem or death caused by, or associated with, a device, if that effect, problem, or death, was not previously identified in a nature, severity, or degree of incidence in the investigational plan or application (including a supplementary plan or application), or any other unanticipated serious problem associated with a device that relates to the rights, safety, or welfare of subjects. (21 CFR 812.3(s))
Device Deficiency	Inadequacy of a medical device with respect to its identity, quality, durability, reliability,

Term	Definition
	
usability, safety or performance.
 
NOTE 1: Device Deficiencies include malfunctions, use errors and inadequacy in the information supplied by the manufacturer including labeling.
 
NOTE 2: This definition includes device deficiencies related to the investigational medical device or the comparator. (ISO 14155:2020, 3.19)

High-Risk PE	
Per ESC guidelines 2019: High-Risk PE determined by hemodynamic instability, PESI III-V or sPESI ≥ 1, RV Dysfunction, and Elevated cardiac troponins.
 
Note Definition of hemodynamic instability, which delineates acute high-risk pulmonary embolism (one of the following clinical manifestations at presentation). 1. Cardiac Arrest: Need for cardiopulmonary resuscitation, 2. Obstructive Shock: Systolic BP < 90 mmHg or vasopressors required to achieve a BP ≥ 90 mmHg despite adequate filling status AND End-organ hypoperfusion (altered mental status; cold, clammy skin; oliguria/anuria; increased serum lactate), OR 3. Persistent Hypotension: Systolic BP < 90 mmHg or systolic BP drop ≥ 40 mmHg, lasting longer than 15 min and not caused by new-onset arrhythmia, hypovolemia, or sepsis.

Intermediate High-Risk PE	
Per ESC guidelines 2019: Intermediate High-Risk PE determined by no hemodynamic instability, PESI III- V or sPESI ≥ 1, RV Dysfunction, and Elevated cardiac troponins.

Intermediate Low-Risk PE	
Per ESC guidelines 2019: Intermediate Low-Risk PE determined by no hemodynamic instability, PESI III- V or sPESI ≥ 1, and 1 or none of the following: RV Dysfunction; Elevated cardiac troponins.

Patient/ Subject	
Participants in the study.

Recurrent PE	
Symptomatic worsening from baseline of the embolism that was successfully treated with the index procedure with documentation of a change on CTPA or other suitable imaging modality, as determined by the independent Medical Monitor.

Signature Page for VV-TMF-35809 v1.0

Reason for signing: Approved	Name: [name] Role: Approver Date of signature: 06-Sep-2023 13:43:37 GMT+0000
Reason for signing: Approved	Name: [name] Role: Approver Date of signature: 06-Sep-2023 15:15:32 GMT+0000
Reason for signing: Approved	Name: [name] Role: Reviewer Date of signature: 06-Sep-2023 18:22:33 GMT+0000
Reason for signing: Approved	Name: [name] Role: Approver Date of signature: 07-Sep-2023 13:13:07 GMT+0000

Signature Page for VV-TMF-35809 v1.0
